7.2 Birth Defect Evaluation

The Registry retains the services of a consultant birth defect evaluator, a physician with expertise in genetics and the evaluation and classification of birth defects. Upon Registry receipt of a case report of a birth defect the report (without provider information) is transmitted to the evaluator within 5 working days for individual case evaluation. This review includes identification of specific aspects of the case for further inquiry from the reporter(s), and clarification and classification of the defect(s) reported in accordance with the classification conventions of the MACDP (CDC, 1998) and a classification system, developed by Scheuerle (Scheuerle and Tilson, 2002) to increase the ability to generate potential signals. In addition, the review includes a temporality assessment with is a determination of the potential relevance of timing of exposure to the event(s) reported.

The birth defect evaluator assessment includes the following:

- Cases that are prospectively reported and deemed evaluable The evaluator may assess a report as "pending further information" if more information is needed to determine the etiology of the defect and/or the temporality. However, if no further information is received despite repeated attempts, the evaluator makes an assessment based upon available information.
- Cases reported retrospectively (i.e., after an abnormal condition has been noted on a prenatal test and/or for which a defect was noted at outcome) The evaluator makes an assessment on the defect and temporality with the information available at initial review. However, if follow-up questions are requested and responses received later, the evaluator re-evaluates the case.

The assessments of temporality with the Registry drug exposure are classified as one of the following:

- Pending
- The development of this defect and the timing of the exposure to drug cannot rule out a possible association
- No temporal association
- Unable to assess temporality
- Defect with known cause, temporality may be irrelevant
- Pathogenesis of this defect has yet to be defined specifically enough to assess temporality
- Not a defect

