5.6.2 Information Collected at Pediatric Follow-up

Infant at outcome

- Date of follow-up evaluation
- Current age of infant (at the time of assessment)
- Gender
- Gestational age at birth
- APGAR scores at birth
- Birth weight, length, head circumference and corresponding population-based percentiles
- Birth defect(s) and details, if noted
 - Type of birth defect(s)
 - Attribution to Savella drug therapy
 - Other factors that might have contributed to the outcome
 - Defect absent/present on pre- or post-natal test
- Chromosomal abnormalities and details, if noted
- Immediate post-natal health problems requiring resuscitation, admission to the neonatal intensive care unit (NICU)
- Medications
- Surgical interventions required of pre-term infants
- Other serious infant adverse outcomes noted on physical examination
 - Evidence of alterations in fetal/infant growth (e.g., intrauterine growth restricted, small for gestational age, etc.)
 - Presence of functional deficit (e.g., poor muscle tone, abnormal reflexes)
 - Presence of biochemical abnormality
 - Presence of transient or infectious conditions
 - Symptoms of poor neonatal adaptation (i.e., neonatal withdrawal)
 - Persistent pulmonary hypertension of the newborn

Infant at 4 and 12 months

- Date of follow-up evaluation
- Current age of infant (at the time of assessment)
- Birth weight, length, head circumference and corresponding population-based percentiles
- Birth defect(s) detected since last assessment and details, if noted
 - Type of birth defect(s)
 - Attribution to Savella drug therapy
 - Other factors that might have contributed to the outcome
 - Defect absent/present on pre- or post-natal test
- Chromosomal abnormalities and details, if noted
- Medications
 - Other serious infant adverse outcomes noted on physical examination

- Evidence of alterations in infant growth
- Presence of functional deficits
- Developmental delays

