5.7.2 Information Collected at Targeted Follow-up

- Details of the birth defect, chromosomal abnormality, or other condition warranting teratology follow-up.
 - The Targeted Follow up form is individualized to the unique history and presentation of each potential defect case.
 - The specific term used to describe the condition under review (i.e, birth defect, chromosomal abnormality, or other condition) is entered on the Targeted Follow up form,
 - Specific questions requested by the sponsor and/or the birth defect evaluator reviewing the case are also entered on to this form.
 - Etiology
 - Outcome attribution

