7.1.2 Birth Defect

The Registry adopts the term "birth defect" for an abnormality usually referred to as a "congenital anomaly" and defines birth defect as follows:

• Any major structural or chromosomal defect diagnosed with signs/symptoms, using the CDC MACDP classification of birth defects (CDC, 1998).

On a case-by-case basis, subject to independent review, clusters of two or more minor abnormalities may in combination constitute a birth defect, even if the outcome of each event alone would not constitute a birth defect according to the MACDP classification. Defining two or more minor defects as a birth defect case is used to increase the sensitivity of pregnancy databases (Scheuerle and Covington, 2004). The presence of multiple minor defects has been shown to increase the likelihood that a major defect or syndrome exists (Leppig et al, 1987, Holmes et al, 1987). To maintain as much consistency with the CDC birth defect surveillance system as possible without missing a potential signal, only cases meeting the MACDP criteria and those with at least two minor defects are included for analysis. Cases with two minor anomalies will trigger further investigation by the registry's birth defect evaluator; the determination of the birth defect evaluator would then decide whether the specifics of any particular case merit its inclusion as a birth defect case. All infants with three or more minor anomalies will be counted as a birth defect case.

The inclusion of cases with minor defects is a conservative approach with the potential to inflate point estimates and enhance signal detection. Individual minor abnormalities are listed in the report but are not included in the analysis of defects.

Under certain circumstances, structural or chromosomal defects detected in the prenatal evaluation of a pregnancy or in the gross or pathologic examination of an abortus, fetus, or deceased infant, that would not otherwise be included in the primary analysis following normal protocol procedures, may be included in a subsequent analysis to increase the sensitivity of Registry monitoring. Such determinations are made on a case-by-case basis and are subject to independent review.

The CDC guidelines disqualify as birth defects:

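### The evaluator decides whether two-minor-anomaly reports count in the same unmasked review that assesses Savella timing; case status should be locked first

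*Protocol*

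**What the plan says.** Protocol 7.2 names a single adjudicator: "The Registry retains the services of a consultant birth defect evaluator". On what is withheld, it says that "the report (without provider information) is transmitted to the evaluator within 5 working days for individual case evaluation". The evaluator classifies the defect under the MACDP conventions and an organ-system scheme. The section then adds: "In addition, the review includes a temporality assessment with is a determination of the potential relevance of timing of exposure to the event(s) reported". No order of the two steps is given, and neither is locked before the other. The list of temporality outcomes has seven entries, and one of them, *Not a defect*, is a statement about case status and not about timing.

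Protocol 7.1.2 sets what counts. Major defects follow the MACDP classification. For three or more minor anomalies the rule is automatic: "All infants with three or more minor anomalies will be counted as a birth defect case". For exactly two, "the determination of the birth defect evaluator would then decide whether the specifics of any particular case merit its inclusion as a birth defect case". No criterion is attached. The same section qualifies minor clusters in general: "On a case-by-case basis, subject to independent review, clusters of two or more minor abnormalities may in combination constitute a birth defect". The Glossary repeats both statements. Who carries out the independent review, when, and with what information is not stated. Sections 7.3 and 12.1 also have the SAC review individual defect cases each year, again with no mention of masking.

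The forms collect Savella start and stop information and dose (5.3.1, 5.4.2) and the reporter's view on causation (5.4.2, 5.5.2 and 5.6.2; in the last, "Attribution to Savella drug therapy"). The Targeted Follow-up form carries an outcome attribution item, and of that form 5.7.2 says: "Specific questions requested by the sponsor and/or the birth defect evaluator reviewing the case are also entered on to this form".

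**The concern.** Every Registry pregnancy is exposed, so exposure itself cannot be masked. What varies between reports is when exposure occurred and what the reporter thought of it, and both can be withheld. An evaluator who knows that exposure fell in organogenesis may be readier to count a borderline pair of minor anomalies, or less ready when it did not. The opposite tendency is also possible. The protocol neither directs this nor prevents it.

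Two results could be affected. One is the count in the primary prevalence (8.5.1), which is compared with MACDP. The other is the summary of birth defect rates by earliest trimester of exposure (8.5.1, 8.5.2), which 8.2 motivates by the first-trimester origin of most structural defects. If timing informs case status, a first-trimester excess, or its absence, could partly reflect classification. MACDP as described in 8.3 finds cases by active search and record abstraction, and no step that weighs a drug's timing is described.

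**Working it through.** **The plan's own figures (8.4).**
- Expected live births: 350 × 0.62 × 0.90 = 195.3, given in the protocol as 196.
- Exact binomial test, N = 196, null 2.78%, alternative 6.95%, two-sided 5%. The smallest upper cutoff with a tail of at most 0.025 is 11 cases: P(X ≥ 11 | 2.78%) = 0.0221 and P(X ≥ 11 | 6.95%) = 0.807. The stated 80% power reproduces.

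**Weight of one decision.**
- Expected cases at the MACDP rate: 196 × 0.0278 = 5.45, or about 5.4.
- Change in the rate for one case: 1/196 = 0.51 percentage points.
- Exact (Clopper-Pearson) 95% intervals: 10/196 = 5.10%, interval 2.47% to 9.18%, which includes 2.78%; 11/196 = 5.61%, interval 2.83% to 9.82%, which excludes it.

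**How often that boundary is in play.**
- If the true rate is 2.78%, P(X = 10) = 0.0487 − 0.0221 = 0.027.
- If it is 6.95%, P(X = 11) = 0.807 − 0.715 = 0.092.
- On the low side there is a similar step between 0 and 1 case: P(X = 0 | 2.78%) = 0.004, and P(X ≤ 1 | 2.78%) = 0.026, just above 0.025. It bears on a conclusion of fewer defects than MACDP, not of an excess.

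**Sensitivity.** The protocol does not say how many two-minor-anomaly reports to expect. Taking 1 to 3 as an assumed range:

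| Discretionary cases | Chance of ≥ 11 at 2.78% if added | Power at 6.95% if left out |
|---|---|---|
| 0 | 0.022 | 0.807 |
| 1 | 0.049 | 0.715 |
| 2 | 0.098 | 0.609 |
| 3 | 0.182 | 0.497 |

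The table shows what such decisions could do if all went one way. It does not predict a bias.

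**What the evaluator must see.** A judgement on timing cannot be made without exposure dates, so the review in 7.2 necessarily includes them. That attribution and sponsor questions are also in the packet is an inference: the forms collect them, and only provider information is said to be removed.

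**The case against.** Several points against the concern are fair.

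- *Other eyes see these cases.* Section 7.1.2 makes minor clusters subject to independent review, and the SAC assesses individual cases. A reader might infer that one person alone settles case status, and the text does not support that. But the independent review is undefined, neither layer is stated to be masked, and the SAC includes sponsor members (7.3). These layers add review without keeping exposure timing out of it.
- *Nothing links timing to case status.* Section 7.2 lists classification first and adds temporality afterwards. A reader might infer that the protocol tells the evaluator to count by timing. It does not. The weakness is that the order is not fixed and timing is not excluded from the case specifics the evaluator may weigh.
- *The packet's contents are presumed.* This stands for attribution and sponsor questions. It does not stand for exposure dates.
- *The discretion is narrow.* This stands. Major defects follow MACDP, and three or more minor anomalies count automatically. Under 7.1.2 the case-by-case prenatal and pathology findings feed a subsequent analysis. A reader might take *Not a defect* as a power to drop any report, but no section says that it removes a case meeting the MACDP criteria.
- *Including minor clusters is conservative.* Section 7.1.2 says so of inclusion. That does not cover leaving out a two-anomaly case, which lowers the count.
- *The 10 versus 11 step is a knife-edge.* This also stands. Any single decision matters there, and the chance of being there is small.

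**Conclusion.** The point holds in a limited form. Classification and the assessment of Savella timing are combined in one review by one evaluator, who has uncriterioned discretion over reports of exactly two minor anomalies, and no stated safeguard masks timing. The effect is confined mainly to those clusters, and its direction and size are unknown. One decision moves the primary rate by 0.51 percentage points. It changes a conclusion of excess over MACDP only at the boundary of 10 and 11 cases, where the chance of sitting is about 0.027 at the MACDP rate (exactly 10) and 0.092 at 6.95% (exactly 11). The split by trimester is also exposed, but the protocol gives no numbers per trimester from which to size that.

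The documents do not show that the primary estimate is biased. Nor is there an exposed-versus-unexposed contrast within the Registry that could be distorted. The figures assume 196 live births, the 2.78% comparator and the exact methods in 8.4 and 8.5.1. This is an inexpensive improvement to adjudication, not a flaw that invalidates the design.

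**What to change.** In 7.2, split the review into two recorded steps by the same evaluator.

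1. **Classify and lock.** Use a packet without Savella dates, dose and reporter attribution. Keep every clinical detail of the defect, including gestational age at birth (needed for the prematurity exclusions in 7.1.2) and clinical answers to follow-up questions, whoever asked them. Record case or non-case and lock it.
2. **Assess temporality.** Release the exposure data only then.

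Allow a later change of status only for new clinical facts about the defect, and log it. Apply the same masking to any independent review or SAC decision that can change case status, and say in 7.1.2 who carries out the independent review. Move *Not a defect* from the temporality list to the classification step. In 8.5.1, report the prevalence with and without the discretionary two-minor-anomaly cases.

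The cost is protocol wording and one more handling step per case, with few cases expected. The Coordinating Center already removes provider details before sending a report, and no extra evaluator is needed. Prompt reporting of defects to the sponsor under 7.3 is unchanged.

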7.3 Monitoring of Outcomes and Signal Detection

The data are reviewed regularly by the staff of health professionals at the Registry Coordinating Center for the appearance of any unusual events or unexpected numbers of specific events. All reports of defects are transmitted promptly to the Sponsor for their independent and immediate review and further regulatory reporting. Additionally, any other fetal, neonatal, or maternal adverse events received by the Registry, are also transmitted to the Sponsor for safety surveillance management and processing.

A Scientific Advisory Committee (SAC) oversees the scientific affairs of the Registry, including its on-going monitoring of transactions. The SAC is composed of recognized experts in the fields of teratology, epidemiology, maternal and fetal medicine, and fibromyalgia, from academia, private practice, government or other agency, and the Sponsor company. The SAC convenes annually to review all individual case reports received in the interim and the overall accumulation of Registry experience, as well as to review Registry processes, awareness activities, and the analysis plan. The SAC is also available for *ad hoc* consultation, data review, and advice.

The intent of the Registry is to determine whether there is a signal that might indicate a potential risk for major birth defects in the offspring of women following exposure to Savella during pregnancy. Therefore, it is necessary to monitor the cumulative data to

detect potential signals or patterns, to evaluate them, and to determine the necessary course of action when a signal is noted. The Registry may never have sufficient power to detect a risk for a particular rare outcome to Savella. However, the Registry SAC has adopted a plan developed by the Antiretroviral Pregnancy Registry for determining what constitutes a signal for a birth defect, how it is reviewed, and what action might be taken should such a signal be seen (Covington et al., 2004). For example, the "Rule of Three" convention specifies that once 3 similar birth defects have accumulated with any specific exposure or exposure combination, these cases are flagged for immediate review. The likelihood of finding three of any specific defects in a cohort of <600 by chance alone is less than 5% for all but the most common defect classes (i.e., those occurring with a rate of <1/700). To enhance the assurance of prompt, responsible, and appropriate action in the event of a potential signal, the Registry employs the strategy of "threshold" based on the Council of International Organizations for the Medical Sciences (CIOMS, 1999). The threshold for action is determined by the extent of certainty about the cases, driven by statistical considerations, and tempered by the specifics of the cases.

In addition, the evaluator reviews all birth defects in aggregate to identify any possible patterns reported. Should a potential pattern occur, it is discussed at the annual SAC meeting. However, if at any time discussion prior to the annual meeting is deemed necessary, a teleconference or meeting would be scheduled. Once a potential signal is identified the component cases can be evaluated individually to determine if there is cause for concern.

Thus, the Registry Staff, along with consultants, review, on an ongoing basis, between periodic meetings of the SAC, all individual reports and the cumulative collection of reports for signals of potential problems. The SAC meets annually and more frequently, if an issue arises, to review individual and aggregate data.

8. STATISTICAL CONSIDERATIONS

8.1 Analysis Population

The primary population for analysis includes prospective evaluable cases that are not "lost to follow-up" (i.e., cases with appropriate outcome information and meeting the minimum criteria for evaluation). Retrospective cases are reviewed and reported separately.

8.2 Analysis Parameters for Birth Defects

Pregnancy outcomes are categorized as live birth (full-term or pre-term), stillbirth, spontaneous abortion, induced abortion (elective or therapeutic), ectopic pregnancy, and molar pregnancy. Most structural defects have their origins in the first trimester of pregnancy; the period of organogenesis. Therefore, the outcome data (i.e., birth defects and other pregnancy outcomes) may be stratified by the earliest trimester of exposure to Savella (first trimester, second trimester, and third trimester).

Gestational weeks are calculated beginning from the first day of the LMP when it is considered to be a reliable predictor of the EDD. However, if a CEDD is available (e. g., by ultrasound), the CEDD is preferred for calculating gestational weeks. The second

trimester begins at 14 weeks and 0 days, and the third trimester begins at 28 weeks and 0 days.

Descriptive statistics are the primary approach for summarizing data from this pregnancy registry. Confidence intervals are provided for purposes of estimation and are not used for statistical inference.

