Design	This is a prospective, observational, exposure-registration and follow-up registry of women and their offspring exposed to Savella during pregnancy and among infants during the first year of life.				
Patient Population	Women exposed to Savella at any time during pregnancy, beginning on or after the first day of the last menstrual period (LMP).				
Procedures	Registry enrollment is voluntary and initiated by pregnant patients or their healthcare providers (HCP). Patient-initiated reports must be verified by the HCP. Enrollment should occur as early in pregnancy as possible, preferably before any prenatal testing has occurred; however, enrollment at any time during pregnancy is allowed. Near the estimated date of delivery, the Registry prompts the HCP to provide pregnancy outcome data. If a live birth is reported, the Registry conducts follow-up with the infant's HCP at outcome, 4 months, and 12 months of age. If a birth defect is indicated, the Registry requests additional targeted follow-up information from the HCP. Data are collected on exposure to Savella,				

	potential confounding factors, pregnancy outcome, and pediatric outcome for all live born babies. Cases are reviewed and classified according to type of birth defects. Adverse event cases are forwarded to Allergan.
Comparison Groups	Given the inherent difficulties in identifying a comparison group, several different methods may be used. First, the prevalence of birth defects are compared to the prevalence observed in the Centers for Disease Control's (CDC) population based birth defects surveillance system, the Metropolitan Atlanta Congenital Defects Program (MACDP). The most recent five-year prevalence rate of 2.78% (6945 cases with birth defects / 249,999 live births) from 1999 to 2003 is used (Correa et al., 2007). The methods and patient population in this Registry differ from those used in the CDC MACDP and therefore it may not be the most appropriate comparator. Second, the prevalence of birth defects may be compared to published data from other studies, if available at the time of analysis.
	The Registry is committed to identifying other appropriate comparison groups and continues to research the literature and explore other sources to obtain appropriate comparators.

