2. PURPOSE AND RATIONALE

The purpose of Allergan's Savella Pregnancy Registry (Registry) is to monitor pregnancies exposed to Savella (milnacipran HCl) to determine the risk of birth defects. Because Savella is commonly used among reproductive age women, this pregnancy registry has been established to prospectively assess the birth outcomes of babies born to women that are exposed to Savella during pregnancy. The lack of human fetal safety data concerning this product makes such a monitoring system an important component of epidemiologic research on the safety of Savella. Due to the lack of human data regarding fetal safety, the Registry is primarily exploratory.

The primary objective of the Savella Pregnancy Registry is:

• To estimate the prevalence of major congenital anomalies among offspring of women exposed to Savella during pregnancy.

The secondary objectives are

- To estimate the prevalence of full-term live births (≥37 weeks), pre-term live births (<37 weeks), recognized spontaneous abortions, stillbirths, induced abortions (elective and therapeutic), chromosomal abnormalities, and minor congenital anomalies
- 2) To summarize
- Serious pregnancy complications and maternal adverse events
- Adverse pregnancy outcomes
- Serious adverse outcomes observed during the first year of life in infants born from exposed pregnancies, including alterations in fetal/infant growth, presence of functional deficits, biochemical abnormalities, transient or infectious conditions, symptoms of poor neonatal adaptation (i.e., neonatal withdrawal), and persistent pulmonary hypertension of the newborn

3. **REGISTRY DESIGN**

This is a prospective, observational, exposure-registration and follow-up registry of women exposed to Savella during pregnancy. The Registry is strictly observational; the schedule of patient visits and treatment regimens are at the discretion of the treating physician. HCPs submit patient data that are routinely collected and documented in the patient's medical record.

4. **REGISTRY POPULATION**

The Registry population includes women with any Savella exposure during pregnancy, defined as exposure on or after the first day of the LMP. Women must be \geq 18 years of age and reside in the US.

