4.2 Minimum Criteria for Registry Enrollment

In addition to meeting the eligibility criteria, the following information must be provided in order to qualify for Registry enrollment:

- Sufficient data to establish in which trimester of pregnancy the exposure to Savella first occurred (i.e., first, second or third trimester)
- Sufficient information to determine whether the pregnancy is prospectively or retrospectively registered (i.e., whether the outcome of pregnancy was known at the

time of first contact with the Registry)

- Date the pregnancy exposure is reported to the Registry
- Source of the report (HCP or pregnant patient)
- Full contact information (name, address, phone number, etc.) for the patient and HCP willing and able to provide accurate pregnancy-related information \

Reported cases that do not meet the minimum criteria for Registry enrollment are deemed invalid. Section 6.3 details follow-up procedures for obtaining necessary data.

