5.3.1 Information Collected at Registration

Reporter Information

- Reporter contact information
- Permission to contact the HCP (if pregnant patient reporter)
- Contact information for two additional personal contacts living outside the patient's home will also be requested. Patients unwilling to provide contact information for family members or friends may use HCPs (e.g., obstetric HCP, prescriber, etc).

Maternal Information

- LMP
- Estimated date of delivery (EDD by LMP)
- Corrected estimated date of delivery (CEDD) (e.g., by ultrasound), if available
- Age (at conception) and ethnic origin
- Whether or not the patient has enrolled in this Registry for a previous pregnancy

Maternal Obstetrical History

- Number of previous pregnancies
- Number of live births
- Number of spontaneous fetal losses, includes number of spontaneous abortions and number of stillbirths

- Number of ectopic pregnancies
- Number of induced abortions
- Number of molar pregnancies
- Number and type of previous congenital anomalies among offspring
- Maternal and paternal family history of birth defects
- Contributing factors to previous adverse pregnancy outcomes or significant previous pregnancy complications

Prenatal Tests

- Type of test, date of test, and gestational age at the time of testing for all prenatal tests including obstetrical dating ultrasounds, if applicable.
- Type of prenatal test (diagnostic or screening) for aneuploidy or fetal anomalies
- Description of birth defect or abnormality found

Savella Exposure Information

- Clinical indication for Savella exposure (at start of pregnancy)
- Date treatment course began
- Total daily dose with units
- Gestational age in weeks of first exposure
- Gestational age in weeks or date treatment stopped, if applicable

Other Exposures During Pregnancy

- Prescription drugs, over-the-counter medications, and other herbal and/or dietary supplements
- Indication, if applicable
- Total daily dose with units
- Route of administration
- Date treatment course began
- Gestation week the treatment course began
- Gestation week or date treatment stopped, if applicable
- Tobacco use during pregnancy
- Alcohol use during pregnancy
- Recreational drug use during pregnancy

Concurrent Medical Conditions

- Other concurrent medical conditions during pregnancy (including complications of pregnancy such as gestational hypertension, pre-eclampsia, eclampsia, gestational diabetes, etc)
- Date condition began

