8.5.3 Adverse Pregnancy Outcomes

Overall and by-stratum point estimates of rates and 95% confidence intervals will be calculated for the following outcomes:

- Spontaneous abortions
- Stillbirths
- Induced abortions (overall and elective or therapeutic)
- Minor congenital anomalies,

Other adverse pregnancy outcomes among pregnancies exposed to Savella and their live births during the first year of life will be summarized as counts and percentages of the total number of prospective evaluable outcomes. Summaries will also be presented by subgroups including maternal age at conception (<25, 25-35, >35), family history of birth defects, smoking status, and alcohol use during pregnancy. Additional subgroups may be analyzed if deemed appropriate and necessary given the sample size. These other adverse pregnancy outcomes include:

- Functional deficits
- Alterations in fetal growth
- Transient or infectious conditions
- Biochemical abnormalities
- Pre-term infants with findings that persist and require surgical intervention

Strata are comprised by earliest trimester of exposure and potentially other variables as appropriate given the sample size, such as maternal age, history of birth defects, lifestyle variables, comorbidities, and concomitant drug exposures.

All chromosomal abnormalities, whether classified as a birth defect or other adverse outcome, will be displayed in a separate listing.

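### Earliest trimester of exposure cannot show who was still exposed near delivery, so it is the wrong stratum for neonatal withdrawal and persistent pulmonary hypertension, and section 8.5.3 lists neither outcome

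*Protocol*

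**What the plan says.** **Exposure classing.** To enroll, a report must contain "Sufficient data to establish in which trimester of pregnancy the exposure to Savella first occurred" (section 4.2). Section 8.2 allows outcome data to be split on that variable ("birth defects and other pregnancy outcomes) may be stratified by the earliest trimester of exposure to Savella"). Section 8.5.3 fixes it for adverse outcomes: "Strata are comprised by earliest trimester of exposure and potentially other variables". The examples of other variables given there are age, history, lifestyle, comorbidities and concomitant drugs; none concerns when exposure ended. The synopsis applies the same strata to adverse outcomes in the first year of life.

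**Neonatal outcomes.** The secondary objectives in section 2 include "symptoms of poor neonatal adaptation (i.e., neonatal withdrawal), and persistent pulmonary hypertension of the newborn". Section 5.6.2 collects both at the birth assessment. Neither appears in the outcome list of section 8.5.3 or among the infant outcomes of section 8.5.4. The outcomes that 8.5.3 does list as other adverse outcomes are expressed as percentages of all prospective evaluable outcomes.

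**Stop dates.** Section 5.3.1 records "Gestational age in weeks or date treatment stopped, if applicable". Section 5.4.2 asks for it again at the end of the second trimester, and the Summary of Evaluations table has it updated at the outcome contact.

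**Malformations.** The primary population (8.1), the primary denominator (8.5.1) and the power statement (8.4) pool all exposure times. Section 8.2 nevertheless states: "Most structural defects have their origins in the first trimester of pregnancy; the period of organogenesis". The synopsis, 8.5.1 and 8.5.2 commit without condition to reporting defects by trimester; 8.2 says only that this may be done.

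**The concern.** The relevant exposure window depends on the outcome. For structural defects the protocol itself points to the first trimester, and trimester of first exposure is a usable marker. Neonatal withdrawal, by its meaning, presupposes drug exposure up to or close to birth. Trimester of first exposure says nothing about that. A woman on drug at her last menstrual period is classed as first trimester whether she stopped within weeks or continued to delivery.

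A first-trimester stratum for newborn outcomes therefore mixes infants at risk with infants whose exposure ended long before. The reported percentage falls below the risk in late-exposed infants by an amount that cannot be recovered from the table. With the two outcomes also absent from the analysis list, two named objectives have no stated summary, and the default stratum would understate them.

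Malformations raise a milder form of the same issue. Live births to women first exposed after the first trimester enter the rate that is set against 2.78%. If they carry no excess risk, they pull that rate toward the baseline.

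**Working it through.** **1. Neonatal dilution.** Let *q* be the risk in infants exposed near delivery and *g* the share of the stratum still exposed then. If infants whose exposure ended early have about zero risk, reported rate = *q* × *g*. The documents give neither quantity, so these are assumed values:

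| *q* | *g* = 0.8 | *g* = 0.6 | *g* = 0.4 | *g* = 0.2 |
|---|---|---|---|---|
| 30% | 24% | 18% | 12% | 6% |
| 20% | 16% | 12% | 8% | 4% |
| 10% | 8% | 6% | 4% | 2% |

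The proportional loss is 1 − *g* whatever *q* is. The documents state no exposure window for persistent pulmonary hypertension; the formula applies to it only so far as early-ended exposure carries no excess risk.

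**2. The protocol's own sample-size figure (8.4).** Expected live births: 350 × 0.62 × 0.90 = 195.3, stated as 196. With n = 196 and a baseline of 2.78%, the smallest count whose upper-tail probability is at most 0.025 is 11 (tail 0.0221). Power = P(X ≥ 11 | 196, 0.0695) = 80.7%. The stated 80% reproduces.

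**3. What that 80% assumes.** It takes 6.95% as the rate over all 196 live births. Let *f* be the share of live births exposed in the first trimester, and suppose only they carry the 2.5-fold risk. The pooled ratio to baseline is 1 + 1.5*f*, and pooled power is P(X ≥ 11 | 196, 0.0278 × (1 + 1.5*f*)). For first-trimester births alone, n = 196*f* (rounded), the rate is 6.95%, and the critical count is found again by the 0.025 rule. The documents do not give *f*.

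| *f* | Pooled ratio | Pooled power | First-trimester births | Critical count | First-trimester-only power |
|---|---|---|---|---|---|
| 0.9 | 2.35 | 74% | 176 | 11 | 68% |
| 0.8 | 2.20 | 66% | 157 | 10 | 66% |
| 0.7 | 2.05 | 56% | 137 | 9 | 62% |
| 0.5 | 1.75 | 36% | 98 | 7 | 53% |

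Restricting to the first trimester loses about 5 points at *f* = 0.9, changes nothing at 0.8 and gains about 17 points at 0.5. The comparison is uneven because the critical count moves in whole cases.

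**The case against.** **On the neonatal outcomes.** The objective is only to summarize these events. Section 8 plans no comparator or test for them, so there is no contrast to bias. Section 8.5.3 leaves room for further variables and subgroups, and a statistical analysis plan could add late exposure. The absence of a test stands. It does not help the reported percentage, which is the planned product and is the figure diluted. The room for other variables is real, but the protocol fixes only earliest trimester, and a later document would have to add the two outcomes as well as the exposure variable.

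**On malformations.** A reader might infer that the primary malformation analysis is wrong and should be replaced by a first-trimester-only analysis, or that true power is 66% and not 80%. The documents do not support either reading:

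- The primary objective concerns exposure during pregnancy, and so does the FDA request quoted in the Background. The pooled rate answers that question.
- Defects by trimester are already committed to in the synopsis, 8.5.1 and 8.5.2.
- The 80% is stated for an overall prevalence of 6.95% and is correct for it. The lower figures belong to a different alternative and an unknown share.
- Late starters enter the primary rate because eligibility covers any exposure in pregnancy. Classing by earliest trimester is what allows them to be separated.
- Section 8.2 says most structural defects arise in the first trimester, not all, so late-exposed infants cannot be called unaffectable.
- Changing the headline population of a registry already issuing cumulative annual reports would be more than a change of wording.

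All of this stands and limits the malformation part to presentation and a stated assumption.

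**Conclusion.** The point holds for neonatal outcomes. Earliest trimester cannot identify exposure near delivery, and two outcomes that are objectives and are collected are missing from the analysis lists. The understatement equals the share of the stratum whose exposure ended early: 20% of the true rate if 80% were still exposed late, 60% if 40% were. This assumes negligible risk after early-ended exposure, and the shares are illustrative.

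For malformations, the primary population is a defensible choice and the power figure is right as stated. What remains is narrower. Section 8.2 is weaker than the synopsis, 8.5.1 and 8.5.2 on stratification by trimester. Section 8.4 also does not say that its power assumes the 2.5-fold rate across every live birth. If the risk is confined to first-trimester exposures, pooled power falls from 81% to between 74% and 36% over assumed shares of 0.9 to 0.5.

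**What to change.** **Section 8.5.3.** Add poor neonatal adaptation and persistent pulmonary hypertension of the newborn to the outcome list. Tabulate these and alterations in fetal growth among live births, by third-trimester exposure (yes/no), derived from recorded start and stop dates and the 28-week boundary in 8.2. List live births before 28 weeks separately, since they cannot have had third-trimester exposure.

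**Section 5.5.2.** The interim contact falls at the end of the second trimester, so third-trimester status depends on the update at outcome. The Summary of Evaluations table includes that update, but the itemized list in 5.5.2 does not name Savella start and stop dates. Align the two.

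**Section 8.2.** Replace the optional wording with a commitment that matches the synopsis, 8.5.1 and 8.5.2.

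**Section 8.5.1.** Keep the all-exposed rate as primary, and present the first-trimester rate with its exact 95% confidence interval against 2.78% beside it.

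**Section 8.4.** State that the 80% assumes the 2.5-fold rate across all 196 live births, and show power over a range of first-trimester shares.

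**Cost.** Analysis work and protocol wording; the needed dates are already within planned data collection. The downside is extra tables with wider intervals in the smaller strata.
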